Through a biomedical protocol involving dietary intervention and nutritional reinforcement with the T-2 investigational nutritional formulation, formulated for individuals with Down Syndrome (DS), Autism Spectrum Disorders (ASD), and Attention Deficit Disorder (ADD/ADHD), it is anticipated that intestinal dysbiosis, pathogenic burden (bacteria, fungi, yeasts), and oxidative stress will be reduced. This intervention is expected to promote a balanced nutritional state and support the production of key neurotransmitters, thereby contributing to improvements in quality of life, sleep regulation, concentration, cognition, self-regulation, and social interactions. Secondary Hypothesis

Oral administration of T-2 in mice will increase dendritic spines and synapses and improve performance in motor and cognitive tasks.

OBJECTIVES

- Improve compromised metabolic processes inherent to these conditions, as reflected in indicators such as dysbiosis, infections, food sensitivities, malnutrition, thyroid function, and neurotransmitter utilization.
- Strengthen the immune system, reducing allergies, sensitivities, otic and respiratory infections, and gastrointestinal pathogens.

- Reduce oxidative stress, leading to decreased anxiety, improved sleep quality, and enhanced Krebs cycle efficiency.
- Enhance gastrointestinal function and nutrient absorption, assessed through markers such as reflux, cholesterol and triglyceride levels, bowel regularity, stool formation, and improvements in body mass index (BMI).
- Improve quality of life, including stabilization of mood, increased social interactions, and reinforcement of cognitive processes such as attention, adaptability, and concentration.

Secondary Objectives

- Ethnography: Quantify the impact of the nutritional intervention on families of individuals with Trisomy 21, Autism Spectrum Disorders (ASD), and Attention Deficit Disorder (ADD/ADHD), with particular attention to changes in family dynamics across different phases of the study.
- Sleep Physiology: Investigate the relationship between diet and sleep in children with ADD and ASD, evaluating the effectiveness of dietary modification on sleep patterns and expression.

CONTRIBUTION OF THE PROJECT TO ADVANCING KNOWLEDGE IN ITS OWN FIELD AND AREA OF RESEARCH

This project represents the first biomedical protocol in Mexico to investigate neuro-nutrition—defined as dietary intervention combined with nutritional enrichment—in populations with Autism Spectrum Disorders (ASD) and Attention Deficit Disorder (ADD/ADHD), while also expanding upon the findings previously obtained in the first stage of this protocol with individuals with Trisomy 21 (Down Syndrome).

The primary aim is to provide both quantitative and qualitative evidence that disability in individuals with DS, ASD, and ADD extends beyond intellectual impairment into biological domains.

The project further seeks to enhance understanding of the metabolic and physiological characteristics of these populations, thereby informing the design of appropriate therapeutic management strategies.

Finally, it intends to demonstrate that ADD encompasses neurobiological, electrical, and biochemical processes, extending beyond the psychosocial dimensions traditionally emphasized.

METHODOLOGY

Operational Duration

The project will run for a period of 13 months.

Population Description

The estimated total population is 72 individuals between 2 and 35 years of age, divided into three groups based on their neurodevelopmental condition:

- Trisomy 21 (Down Syndrome, DS)
- Autism Spectrum Disorder (ASD)
- Attention Deficit Disorder (ADD)

Each group included between 24 and 27 participants, with more males than females. Ages ranged from 2–33 years for ASD, 2–30 years for DS, and 5–14 years for ADD. Mean ages and BMI values are shown in Table 1.

Participants	ASD (N = 27)	ADD (N = 25)	DS (N = 24)
	Mean (SD)	Mean (SD)	Mean (SD)
Age (years)	2-33 11.51±8.5	5-14 8.8±2.32	2-30 13.7±7.25
Body mass index (kg/m ²)	19.11±3.71	18.41±4.01	21.92±6.27
Men	24	20	14
Women	3	5	10

Table 1. Characteristics of each group

For participants with Autism Spectrum Disorders (ASD), recruitment was conducted at DOMUS Instituto de Autismo A.C., where diagnoses were confirmed using DSM-IV criteria (First et al., 2002). Symptom severity was assessed with the IDEA (Inventario del Espectro Autista-Autism Spectrum Inventory), which evaluates 12 developmental dimensions across four areas and is scored on a scale from 0 to 8. Scores between 70–96 indicate classic Kanner autism, 50–70 correspond to regressive autism, 40–50 reflect high-functioning

autism, and 30–45 indicate Asperger's syndrome (Martos & Morueco, 2007; García-López & Narbona, 2014b). The mean IDEA score for this sample was 63 ± 18 (Table 2).

Diagnostic (DSM-IV)	IDEA (Autism Spectrum Inventory)
ASD N = 27	Classic Kanner Autism (70–96) – 40%
Pervasive Developmental Disorders (PDD):	“Regressive Autism” (50–70) – 40%
Autistic Disorder – 74%	High-Functioning Autism (40–50) – 4%
Pervasive Developmental Disorders, Not Otherwise Specified (PDD-NOS) – 26%	Asperger's Syndrome (30–45) – 16%

Table 2. Diagnosis and IDEA scores in ASD participants

For participants with Attention Deficit Disorder (ADD/ADHD), recruitment was conducted through schools specializing in this condition. Diagnosis was confirmed using the Conners' Parent Rating Scale – Revised (Long Form), which assesses behavioral and learning difficulties, psychosomatic complaints, impulsivity, hyperactivity, and anxiety (Conners, 1999). The Hyperactivity Index was applied, with scores greater than 16 for boys and 12 for girls aged 6–11 indicating clinically significant hyperactivity (Orjales Villar, 1998) (Table 3).

Check list DSM-IV	Hyperactivity Index Conners Revised Scale	
ADD N = 25	Girls (n=4) with suspected ADD (>12)	50 %
	Boys (n=21) with suspected ADD (>16)	33 %

Table 3. Conners' Scale results for ADD participants

For DS, participants came from “CTDUCA Atención Integral de Personas Down IAP” and “Integración Down IAP.” All had karyotype-confirmed diagnoses, with one case of mosaicism.

Population Segregation

Each diagnostic group was further divided into three subgroups:

- Pilot Group: Received 23 g of T-2 twice daily and followed a strict dietary intervention protocol.
- Diet Group: Followed the dietary intervention protocol without supplementation.
- Control Group: Received neither supplementation nor dietary intervention.

The study population (ages 2–35) was further stratified into subgroups A–G (3–30 years) according to developmental stages (*Figure 6: Age distribution*).

Subgroup	Lower limit	Upper limit
A	3	5
B	6	9
C	10	13
D	14	17
E	18	21
F	22	25
G	26	30

Figure 6. Population distribution by age groups

Clinical Evaluation

Clinical follow-ups included parental reports and physical examinations aimed at detecting allergies, food sensitivities, candidiasis, infections, gastrointestinal disturbances, chronic otitis media, and other recurrent conditions. A 25-item checklist was applied, covering digestive, respiratory, dermatological, and systemic indicators.

Laboratory Studies

Laboratory support included:

- Blood count: red/white series, platelets, sedimentation.
- Blood chemistry: glucose, urea, creatinine, uric acid, lipids, triglycerides.
- C-reactive protein: marker of inflammation.
- Serum homocysteine: marker of fat metabolism and oxidative stress.
- Plasma cortisol: indicator of adrenal activity.
- Thyroid panel: T4, free T4, T3, protein-bound iodine, TSH, total cholesterol.

- Stool analyses: coprological, coproparasitoscopic (3 samples).

Some specialized biochemical analyses were conducted at The Great Plains Laboratory (Kansas, USA), led by [name], including:

- IgG Food Allergy Panel (93 foods).
- Comprehensive Organic Acid Test (65 metabolites).
- Urinary peptides from gluten and casein.

Anthropometrics

Weight, height, and BMI were measured monthly, compared against WHO growth standards (BMI-for-age) and Mexican NOM references (NOM-008-SSA2-1993; NOM-174-SSA1-1998).

Ethnography

The study adopted a longitudinal approach using the Sherlock model, combining quantitative and qualitative assessments of personal, functional, and social quality of life. Families underwent three structured interviews (baseline, mid-study, final), recorded in audio and video, with statistical and content analysis applied to results.

Neuropsychology

IDEA Inventory (ASD): Applied to establish severity, guide interventions, and assess treatment impact across 12 dimensions.

Down Syndrome: Cognitive assessments emphasized daily life skills, cognitive processes, and emotional capacities. Recommended tests were culturally and linguistically adapted (Rondal, Perera & Spiker, 2011; Edgin et al., 2010). Tools included:

- **Ages 3–6:** BATELLE developmental inventory (Newborg et al., 1998).
- **Ages 6–35:** NEUROPSI Attention and Memory (Ostrosky et al., 2003), Executive Function Battery (Flores et al., 2008, 2011), computerized neuropsychological tasks (Ostrosky et al., 2003), basic emotion recognition tasks, Barthel Index (Cid-Ruzafa & Damián-Moreno, 1997), and BRIEF executive function scale (Goia et al., 2000).

The neuropsychological evaluation was coordinated by [name] [name], with support from trained psychology interns (4–6 students).

ADD: NEUROPSI Attention and Memory (6–85 years), EDAH (for ADHD), and Conners' Scales (long parent version, 80 items) were applied.

Polysomnography and P300

Polysomnographic assessments included recordings of EEG, EOG, EMG, heart rate, respiratory effort, airflow, oxygen saturation, limb movements, and sleep architecture. Data were analyzed according to international standards and compared with control groups using ANOVA.

Measured variables included total sleep time, wake time, sleep efficiency index, distribution of sleep stages, number of awakenings, apnea–hypopnea index, and periodic limb movement index. Additionally, P300 event-related potentials were incorporated as an independent clinical measure.

All studies were conducted at a specialized sleep clinic in Mexico City, and participants received dietary support throughout the study period.

Family Seminars

To support families and disseminate the objectives of the study, a series of educational seminars was organized. Topics addressed included candidiasis, allergies, biomedical protocols, psychological adaptation to disability, family dynamics, and nutritional interventions (e.g., gluten-free diets, food additives, and cooking classes).

The sessions were delivered by [name] [name], Psychologist [name], and Biochemical Engineer [name].

BENEFITS AND RISKS FOR THE POPULATION

This is considered a minimal-risk study, as supplementation does not pose a health risk and does not involve pharmaceutical compounds.

Risks associated with sample collection, electrophysiological studies, and psychological testing will be managed by the professional staff of the Instituto Mexicano de Medicina Integral de Sueño. In all cases, follow-up will be provided by a multidisciplinary medical

team that includes specialists in Otorhinolaryngology, Psychology, Geriatrics, Dentistry, Pediatrics, Neurology, Psychiatry, Pulmonology, and Internal Medicine.

All participants will receive reports from their clinical assessments, evaluations, and electrophysiological studies, along with specialized counseling. Any conditions requiring medical care will be addressed and followed up by qualified medical professionals.

ASSIGNMENT OF RESPONSIBILITIES: RESEARCH TEAM AND ASSOCIATED ENTITIES

Professional Staff

- [name] [name] – Principal Investigator (CONACYT CVU: 74747)
- [name] [name] – Sleep Physiology Area Leader (CONACYT CVU: 288056)
- I.Q.I. [name] – Technical Coordinator (CONACYT CVU: 392429)
- Eng. [name] – Legal Representative and Administrative Coordinator (CONACYT CVU: 392684)
- Lic. [name] – Project Administrator (CONACYT CVU: 499625)
- I.B. [name] – Biomedical Area Leader (CONACYT CVU: 353604)
- [name] [name] – Neurobiology Area Leader (CONACYT CVU: 39694)
- [name] [name] – Neuropsychological Evaluation for Down Syndrome (CONACYT CVU: 174346)
- Lic. [name] – Neuropsychological Evaluation for ADD (CONACYT CVU: 510484)
- [name] – Ethnographic Area Leader (CONACYT CVU: 510634)

Institutional Site

Instituto Mexicano de Medicina Integral de Sueño

Associated Entities

- Mexico: Olarte y Akle Bacteriólogos, S.A. de C.V.
- United States: The Great Plains Laboratory, Inc.

- Integración Down, I.A.P.
- Domus Instituto de Autismo

PROGRESS CONTROL PLAN

The project is scheduled to last 13 months, from December 2021 to December 2022, and will be divided into two stages of approximately six months each.

Stage I: Design and Intellectual Property Protection

Duration: First Semester

Objectives:

- Confirm the physiological and metabolic similarities documented in the literature across the study populations and design a unified nutritional intervention scheme.
- Determine expected cerebral modifications resulting from the intervention by standardizing the protocol in neurotypical animal models.

Goals:

- Create a homogeneous information base documenting physiological and metabolic affinities among the target populations.
- Obtain audiovisual records of families highlighting quality of life aspects.
- Establish a specialized dataset on sleep habits of individuals with the studied neurodevelopmental disorders.
- Document neuropsychological and behavioral profiles within family, social, and school contexts.

Activities:

- **Bimonthly 1:** Confirm study populations (Down Syndrome, ASD, ADD).
- Assign dietary subgroups (Pilot, Diet, Control).
- Conduct studies of the T-2 investigational nutritional formulation
- Baseline studies including laboratory tests, clinical reviews, anthropometric measures, ethnographic interviews, neuropsychological tests, full polysomnographic records, and P300 potentials.

- Standardize animal model protocol.
- **Month 1:** Start nutritional intervention (diet implementation).
- **Month 4-6:** Report baseline results, documenting biomedical, dietary, familial, cognitive, behavioral, and sleep-related findings. Conduct behavioral tests in animal models.

Expected Results at the End of Stage I (6 months):

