Key findings from the previous study that support extending the nutritional intervention to populations with Autism Spectrum Disorders (ASD) and Attention Deficit Disorder (ADD) included: strengthened immune function with fewer parasitic infections; improved absorption of proteins, calcium, phosphorus, and iron, resulting in higher growth rates compared to controls; healthier cholesterol and triglyceride profiles, thereby reducing cardiovascular risk; more efficient digestion and decreased chronic intestinal inflammation; and improved intestinal motility. In addition, participants demonstrated greater concentration, enhanced attention, and more socially adaptive behaviors.

Building on this evidence, and considering that the theoretical framework of the prior project already encompassed individuals with ASD, the present study aims to explicitly include them as a primary target population, alongside individuals with ADD.

Etiology

The precise causes of Autism Spectrum Disorders (ASD), Down Syndrome, and Attention Deficit Disorder (ADD) remain unclear. Current therapeutic approaches are primarily aimed at alleviating symptoms that compromise quality of life, cognitive performance, and social integration. Although their etiology has not been fully established, these conditions are widely recognized as neurodevelopmental disorders that share significant genetic, immunological, metabolic, and gastrointestinal characteristics.

Genetics

Post-mortem brain studies examining genes associated with these disorders have highlighted immunological convergence rather than differences limited to neurodevelopmental genes. Consistently observed findings include immune system depression and elevated oxidative stress, both of which influence the type and severity of the disorder, as well as the degree of intellectual disability (Lintas, Sacco, & Perisco, 2010).

Mineral deficiencies—particularly calcium, magnesium, zinc, iron, and selenium—have also been linked to immune dysfunction.

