The fermentative activity of *Candida* in protein and carbohydrate metabolism, together with oxidative stress, has been associated with degenerative and autoimmune diseases such as Alzheimer's disease, diabetes, fibromyalgia, and multiple sclerosis. Nutritional control and targeted supplementation may significantly reduce these risks in populations with Down Syndrome, Autism Spectrum Disorders (ASD), and Attention Deficit Disorder (ADD).

The functional sensitivity of these groups also predisposes them to allergic or food sensitivity reactions, which may manifest as behavioral, psychological, and cognitive disturbances.

Quality of Life

Scientific research on quality of life (QoL) has expanded considerably worldwide, ranging from Anglo-European contexts (Roy Brown, 2000) to Latin American settings (Verduzco, 2010). Disability is often conceptualized as the functional and social manifestation of an impairment, medically attributed to a natural accident or condition. However, this framework tends to overlook the subjective and socially constructed dimensions of disability (Ferreira, 2006).

Recognizing QoL within disability contexts now requires greater emphasis on social action and inclusion. Understanding the interrelationship between disability and QoL is fundamental to promoting equitable participation and overall well-being.

Sleep Physiology

ASD and Sleep Disorders

Studies have shown that children with Autism Spectrum Disorders (ASD) frequently experience sleep-wake disturbances, particularly irregular circadian rhythms (Gail, 2004). While many findings are derived from parent-reported questionnaires, objective assessments such as actigraphy and polysomnography have confirmed abnormalities in sleep architecture (Allik & Malow, 2006; Goldman & Souders, 2009). Reported prevalence rates of sleep disorders in ASD range from 44% to 83% (Gail, 2004).

Genetic anomalies affecting melatonin synthesis and signaling are considered central to these disturbances. Clinical studies indicate that melatonin administration can improve total sleep time, reduce sleep latency and nighttime awakenings, and enhance daytime behavior, with minimal adverse effects (Richdale, 1995; Wright, 2010; Rossignol, 2011; Leu, 2010).

ADD and Sleep Disorders

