Proteins are essential nutrients, second only to water in abundance in the human body. They are the fundamental components of muscles, vital organs, blood cells, enzymes, and hormones (Herman, 2009). Structurally, proteins are chains of amino acids; there are 20 in total, 9 of which are essential and must be obtained from the diet.

Animal-based proteins typically provide all essential amino acids in balanced proportions, whereas plant-based proteins require careful combination to achieve adequacy. Protein quality is evaluated through indices such as Biological Value (BV) and the Protein Digestibility Corrected Amino Acid Score (PDCAAS), the latter having been the preferred method of assessment by both the FDA and WHO since 1993.

The primary role of protein is to support tissue repair and maintenance. When consumed in excess, protein can also serve as a precursor for energy production through the Krebs cycle (Meléndez-Hevia, Waddell & Cascante, 1996). Conversely, insufficient intake compromises tissue integrity.

In individuals with Down Syndrome, Autism Spectrum Disorders (ASD), or Attention Deficit Disorder (ADD), metabolic deficiencies—including allergies or sensitivities—may impair the hydrolysis of certain animal proteins (such as casein, albumin, and red meat proteins) as well as plant proteins like gluten (Shaw, 2008).

The whey protein incorporated into the T-2 investigational nutritional formulation provides all essential amino acids with high bioavailability and closely resembles the composition of human breast milk, making it highly efficient and particularly beneficial for individuals with intestinal dysbiosis. As a pure whey protein concentrate, it carries no allergenic risk.

Flaxseed

The use of flaxseed as a functional food dates back centuries, particularly in European bread-making traditions. Modern studies in the United States have confirmed its health benefits. Flaxseed varieties suitable for human consumption include brown and golden,

with an average composition of 41% fat, 20% protein, 28% dietary fiber, 7.7% moisture, and 3.4% ash (Morris, 2007).

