The flaxseed incorporated into the T-2 investigational nutritional formulation is milled golden flaxseed and is sourced from golden flaxseed harvested at peak maturity. Its specialized processing preserves fat micelles and maximizes antioxidant content, particularly lignans, providing 10 mg per gram, equivalent to approximately 30% of the daily antioxidant requirement. Milled golden flaxseed also offers a favorable Omega-6 to Omega-3 ratio (2:3), which supports neurotransmitter production and contributes to overall metabolic balance.

Milk Serum Mineral Complex

Calcium is a vital mineral, with 99% of the body's stores located in bones and teeth. It also plays an essential role in muscle contraction, blood clotting, and nerve transmission. Inadequate calcium intake during childhood and adolescence compromises bone development, as nearly half of total bone mass is formed during these life stages.

The calcium included in the T-2 investigational nutritional formulation is obtained through ultrafiltration of milk serum, a process that preserves its natural nutrient balance. Its composition closely resembles that of human bone. The FDA has recognized several health claims for milk-serum mineral complex, including its role in promoting bone health, supporting postmenopausal women, enhancing calcium absorption, and preventing osteoporosis (Ward, 2007).

Milk-serum mineral complex also demonstrates high solubility in acidic environments, ensuring superior bioavailability. This enhances cellular nutrient uptake and potentiates the absorption of other nutrients present in the T-2 formula.

Short-Chain Fructooligosaccharides (scFOS)

Short-chain fructooligosaccharides (scFOS) are composed of fructose molecules with a terminal glucose unit. They occur naturally in foods such as onions, asparagus, garlic, oats, rye, and artichokes, and are resistant to digestion in the upper gastrointestinal tract. Once they reach the colon, they are fermented by the microbiota and act as prebiotics.

Human studies have demonstrated that scFOS intake can increase bifidobacteria populations up to tenfold, while simultaneously suppressing pathogenic microorganisms such as Clostridia and Candida (Molis et al., 1996; Mitsuoka, Hidaka & Eida, 1987). Their prebiotic role has been formally recognized by both the World Health Organization (WHO) and the Food and Agriculture Organization (FAO) (2001), highlighting their contribution to gut health through selective microbial modulation.

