Although its fungicidal properties are less extensively studied, lactoferrin is known to combat *Candida* infections by acting synergistically with leukocytes to inhibit fungal reproduction. Its antiviral activity is primarily achieved by blocking viral attachment to host cells, thereby preventing entry and replication. This effect has been documented against several viruses, including hepatitis, rotavirus, leukemia viruses, and herpes.

Humans receive their highest dose of lactoferrin through colostrum, the first maternal milk produced after childbirth. Human milk contains the greatest concentration of lactoferrin of all mammalian milks, with colostrum containing approximately three times more than mature milk (Nagasawa, Kiyosawa & Kuwahara, 1972). After human milk, cow's milk provides the next richest source.

The lactoferrin included in the T-2 investigational nutritional formulation is sourced from cow's milk. It is extracted from whey using a process that preserves its bioactivity. Documented properties include immune modulation, stimulation of intestinal cell growth,

antimicrobial action, iron transport, inhibition of intestinal dysbiosis, and suppression of fungal overgrowth in the oral and gastrointestinal tract (Ward, 2006).

Pyridoxine Hydrochloride (Vitamin B6)

Vitamin B6, also known as pyridoxine, is one of the eight vitamins in the B-complex group. Collectively, B vitamins are essential for converting carbohydrates into glucose—the body's primary energy source via the Krebs cycle—and are also involved in lipid and protein metabolism.

Specifically, Vitamin B6 plays a central role in brain development and function. It serves as the primary cofactor for the enzymes delta-5-desaturase and delta-6-desaturase, which are required for the breakdown of omega-6 and omega-3 fatty acids into critical neurotransmitters, including serotonin, epinephrine, norepinephrine, dopamine, melatonin, and gamma-aminobutyric acid (GABA). Together with Vitamin B12, it is also indispensable for the production of erythrocytes (red blood cells) and leukocytes (white blood cells), the latter being key components of the immune system.

Vitamin B6 is metabolized primarily in the liver, jejunum, and ileum, exerting much of its activity through the digestive system before being distributed to other tissues. Functionally, it acts as a coenzyme in the synthesis of hemoglobin, histamine, neurotransmitters, and in the metabolism of lipids, glucose, and amino acids.

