The T-2 formulation includes pyridoxine hydrochloride (vitamin B6).

Systemic Functioning of the T-2 investigational nutritional formulation

The T-2 investigational nutritional formulation acts on multiple metabolic pathways and biochemical processes, not only through the properties of its individual components but also through their synergistic interactions, which enhance systemic balance across organs and tissues.

Isomaltulose, being enzymatically rather than bacterially hydrolyzed, is not a viable substrate for pathogenic microorganisms such as *Candida*. This property reduces parasitic colonization throughout the gastrointestinal tract and helps prevent nutrient malabsorption. In combination with lactoferrin, which provides antimicrobial protection at entry points such as the oral cavity, the investigational formulation establishes protective conditions from ingestion onward.

The strong glycosidic bond of Isomaltulose ensures sustained energy release, avoiding abrupt glucose spikes and subsequent hypoglycemic crashes. Unlike sucrose, which is rapidly fermented by bacteria, Isomaltulose supports a balanced supply of glucose and glycogen, stabilizes insulin secretion, and reduces anxiety, thereby contributing to improved learning, concentration, emotional regulation, and appetite control.

Its synergy with milled golden flaxseed flaxseed further promotes fat metabolism by encouraging the body to utilize fat reserves when carbohydrate absorption is slowed. Together, Isomaltulose, flaxseed, and scFOS promote the restoration of intestinal balance by stimulating the growth of beneficial bifidobacteria and lactobacilli, improving nutrient absorption, and optimizing osmolarity (170–295 mOsm/L).

Whey protein concentrate whey protein supports the repair of intestinal lesions caused by *Candida* and *Clostridia*. This is particularly relevant given that the small intestine produces up to 95% of the body's serotonin and 50% of its dopamine (Manocha et al., 2012; Gershon, 1999; Mirre, 2012). By restoring intestinal integrity, Whey protein concentrate enhances neurotransmitter production, with synergistic effects amplified by milk-serum mineral complex calcium and flaxseed-derived vitamin K, both of which are essential for bone health and blood coagulation.

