Milled golden flaxseed flaxseed provides 1.09 g of dietary fiber per serving, which contributes to improved intestinal motility and helps maintain microbiota balance. Its fatty acid profile ensures the sequential metabolic conversion of oleic acid (omega-9), linoleic acid (omega-6), and alpha-linolenic acid (omega-3) into arachidonic acid, EPA, DHA, and prostaglandins, thereby supporting inflammatory regulation and cerebral blood flow.

Dosage and Administration

Participants will be instructed to take 23 g of the T-2 investigational nutritional formulation, twice daily, dissolved in 250 ml of liquid.

For the study population (Trisomy 21, ASD, and ADD/ADHD), it is recommended that the investigational formulation be prepared with Casein-free beverage, which is casein-free and enriched with probiotic fiber. However, it may also be consumed with other liquids—including cow's milk, plant-based beverages, coffee, tea, water, or natural juice—without altering its properties. The formulation can be taken hot, cold, or warm.

The first daily dose should be consumed upon waking, ideally 30–60 minutes before breakfast. The second dose should be taken in the afternoon, approximately two hours before sleep, regardless of dinner timing.

Ethnography

Studying quality of life (QoL) in families with a member diagnosed with Autism Spectrum Disorders (ASD), Attention Deficit Disorder (ADD/ADHD), or Trisomy 21 (Down Syndrome) is a central aspect of this research. Such analysis makes it possible to assess not only the progress of participants undergoing nutritional intervention but also the broader impact on family dynamics.

In recent years, QoL has gained increasing importance due to the limited opportunities for social, family, and leisure activities, particularly in households managing neurodevelopmental conditions. Evidence from the initial phases of this line of research has demonstrated that nutritional interventions can strengthen specific abilities in individuals with disabilities while also enhancing the overall well-being of their families.

These outcomes justify expanding the scope of investigation from ethnographic exploration to sociological analysis, providing valuable insights into the cognitive and behavioral evolution of participants, as well as the adaptive changes within their families over the course of one year.

Sleep Physiology

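### The protocol says T-2's whey has no allergenic risk and supplementation no health risk, although it calls its own groups prone to food reactions, and its named managed risks omit T-2

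*Protocol*

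**What the plan says.** Two statements in the protocol are absolute.

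- **Whey Protein Concentrate (Justification).** The section closes on the T-2 whey with "As a pure whey protein concentrate, it carries no allergenic risk". Neither this sentence nor the one before it carries a reference.
- **Benefits and Risks for the Population.** The study is rated minimal-risk on two grounds: that supplementation is harmless to health, and that no pharmaceutical is involved. The risks to be managed by staff are those of sampling, electrophysiology and psychological testing.

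Other text bears on them.

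- **Oxidative Stress and Allergies (Background).** The functional sensitivity of the three diagnostic groups "also predisposes them to allergic or food sensitivity reactions, which may manifest as behavioral, psychological, and cognitive disturbances".
- **Whey Protein Concentrate, preceding paragraph.** In these groups, metabolic deficiencies, among which it counts allergies and sensitivities, "may impair the hydrolysis of certain animal proteins (such as casein, albumin, and red meat proteins", as well as gluten.
- **Milk Serum Mineral Complex.** The calcium source "is obtained through ultrafiltration of milk serum".
- **Lactoferrin.** "The lactoferrin included in the T-2 investigational nutritional formulation is sourced from" cow's milk.
- **Dosage and Administration.** "Participants will be instructed to take 23 g of the T-2 investigational nutritional formulation, twice daily".

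**The concern.** The protocol describes a population prone to reactions to food, gives part of it a new food product, and declares that product free of risk. That premise supports the study's risk rating, so it needs either evidence or qualification.

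Interpretation is also at stake. By the protocol's own account, food reactions can show up as disturbed behavior, mood or cognition. The study measures those same domains as outcomes (Objectives; Progress Control Plan, Stage II). If nobody is asked to consider T-2 as a cause, a reaction in a Pilot participant could be put down to the underlying condition or counted as lack of benefit.

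**Working it through.** The protocol gives no figure to reproduce, so the check compares its statements and asks whether anything closes the gap.

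**1. Are the two statements supported?**
- The citations in the whey section attach to other points (protein function, energy metabolism, impaired protein handling), not to whey allergenicity.
- The reference list holds ingredient-level safety material: a review of biological and toxicological studies of isomaltulose, a European authorisation of isomaltulose, and two GRAS response letters whose titles name no substance. None is cited for whey or for the complete formula.
- The paragraph that opens "Key findings from the previous study that support extending the nutritional intervention" lists benefits and reports no tolerability result.
- Stage I lists studies of T-2 as an activity, without content or results.

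**2. Do they agree with the rest of the protocol?** A general predisposition to allergic or food-sensitivity reactions is hard to square with a claim of zero risk for a food product given to the same people. The claim covers one ingredient in the first statement and the whole supplement in the second.

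**3. What is the exposure?**
- Daily amount in the Pilot subgroup: 2 × 23 g = 46 g of powder. The milk-protein content is not given.
- Named ingredients: seven in the Sleep Physiology part of the Justification, plus one more ("The T-2 formulation includes pyridoxine hydrochloride (vitamin B6"), so 7 + 1 = 8. Milk-derived: whey concentrate, milk-serum mineral complex and lactoferrin = 3. This is a count and says nothing about share by weight.
- Subgroup sizes and reaction rates are not given, so no expected number of reactions can be computed.

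**4. What already exists that could catch a reaction?**
- Clinical Evaluation: examinations that look for allergies, food sensitivities and gastrointestinal problems, and a 25-item checklist covering digestive, respiratory, skin and systemic signs.
- Laboratory Studies: an IgG panel of 93 foods.
- Benefits and Risks: a multidisciplinary team and a promise to attend to any condition that needs care.
- Stage II: biomedical outcomes analysed across groups, supplemented set against non-supplemented participants, and a technical report that includes changes in dietary allergy and sensitivity.

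**5. Is any of this tied to T-2 as a possible cause?** Not in the text shown. The Objectives mention allergies and sensitivities only as things expected to fall.

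**The case against.** The strongest reply is that this is a matter of wording. Allergy signs are looked for, a food panel is run, care is promised whatever the cause, and the Stage II report on allergy and sensitivity speaks of changes, which covers worsening as well as improvement. Detailed safety tables usually belong in a statistical analysis plan, which is not at hand. Most of this stands. A reader might infer that reactions would go unseen or untreated; the protocol does not support that. What is missing is attribution to T-2, and nothing listed corrects the two absolute statements.

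A second reply is that the protocol does not contradict itself about whey. It names casein, albumin, red meat proteins and gluten as difficult, treats whey separately, and speaks there of impaired digestion. This also stands. A reader might infer that the protocol shows the whey to be allergenic. It does not, and that conclusion would need outside evidence. The inconsistency is between a claim of no risk and a stated general predisposition.

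A third reply is that the risk rating has a second ground and that some ingredient safety sources exist. Both are true. It would go too far to say that the rating rests on this premise alone or that no safety evidence is held. The GRAS letters may cover further ingredients.

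Finally, consent and other pages were removed from the copy reviewed. A reader might infer that participants are given no warning about reactions; that cannot be checked.

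**Conclusion.** The point holds as one about the stated risk premise. The claim of no allergenic risk is uncited, and the claim that supplementation is harmless is one of two grounds for the minimal-risk rating. Both are inconsistent with the protocol's account of its own population, and T-2 is absent from the named managed risks.

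No numerical size can be attached. Confounding of a reaction with the behavioral and cognitive outcomes is a possibility that follows from the protocol's own text, not a demonstrated bias. The conclusion assumes that the removed pages do not already name T-2 reactions as a risk. The correction should be made because it concerns participant safety and costs little. It does not call the arms, the dose or the visit schedule into question.

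**What to change.** - **Whey Protein Concentrate.** Cite support for the allergenicity sentence, for example tolerability data from the earlier study if they are held, or replace it with a qualified one.
- **Benefits and Risks for the Population.** Replace the flat statement about the supplement with a qualified one, restate the reason for the minimal-risk rating to match, and add reactions to T-2, including its milk-derived ingredients, to the managed risks.
- **Clinical Evaluation and Stage II deliverables.** Designate the existing 25-item checklist and the allergy and sensitivity report as safety outputs as well, and show new or worsened signs by arm (Pilot, Diet, Control). Pilot against Diet is the contrast most relevant to T-2, since both follow the diet and only Pilot takes the supplement.

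Any clinical rule for a participant with a positive allergy or sensitivity result is for the investigators to set.

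The cost is wording in the affected sections and one extra table from data already collected. The downside is a less favourable risk statement.
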